2.2.2.4 AMG 176 Clinical Experience

AMG 176 is currently being investigated in a phase 1, FIH, multicenter, open-label, dose-expansion study (Study 20150161) in subjects with relapsed or refractory (R/R) AML. For efficacy data in AML subjects, see [Table 2-1](#).

A detailed description of the chemistry, pharmacology, PK, efficacy, and safety of AMG 176 is provided in the Investigator's Brochure.

Table 2-1. Study 20150161 Best Overall Response – Acute Myeloid Leukemia

	Part 3a AMG 176 60 mg/m ² BIW monotherapy (N = 6)	Part 3a AMG 176 120 mg/m ² BIW monotherapy (N = 5)	Part 3b AMG 176 60 mg/m ² QW + azacitidine (N = 5)	Part 3b AMG 176 120 mg/m ² QW monotherapy (N = 5)	Part 4 AMG 176 120 mg/m ² QW + azacitidine (N = 4)	Part 3b AMG 176 180 mg/m ² QW monotherapy (N = 5)	Part 4 AMG 176 180 mg/m ² QW + azacitidine (N = 4)	Part 3b AMG 176 240 mg/m ² QW monotherapy (N = 4)	Part 4 AMG 176 240 mg/m ² QW + azacitidine (N = 6)
Best overall response – n (%)									
CR without minimal residual disease (CR _{MRD-})	0 (0.0)	0 (0.0)	0 (0.0)	0 (0.0)	0 (0.0)	0 (0.0)	0 (0.0)	0 (0.0)	0 (0.0)
Complete remission (CR)	0 (0.0)	0 (0.0)	0 (0.0)	0 (0.0)	0 (0.0)	0 (0.0)	0 (0.0)	0 (0.0)	0 (0.0)
CR with incomplete hematologic recovery (CRI)	1 (17)	1 (20)	0 (0.0)	0 (0.0)	1 (25) ^a	0 (0.0)	0 (0.0)	1 (25)	2 (33) ^a
Morphologic leukemia-free state (MLFS)	0 (0.0)	0 (0.0)	0 (0.0)	0 (0.0)	0 (0.0)	1 (20)	0 (0.0)	0 (0.0)	0 (0.0)
Partial remission (PR)	1 (17)	0 (0.0)	0 (0.0)	0 (0.0)	0 (0.0)	0 (0.0)	1 (25)	0 (0.0)	0 (0.0)
Stable disease (SD) ^b	0 (0.0)	0 (0.0)	0 (0.0)	1 (20)	2 (50)	2 (40)	1 (25)	0 (0.0)	1 (17) ^a
Progressive disease (PD)	0 (0.0)	0 (0.0)	0 (0.0)	0 (0.0)	0 (0.0)	0 (0.0)	0 (0.0)	0 (0.0)	0 (0.0)
Missing	0 (0.0)	0 (0.0)	0 (0.0)	0 (0.0)	0 (0.0)	0 (0.0)	0 (0.0)	0 (0.0)	0 (0.0)

BIW = twice weekly; CRI = complete response/remission with incomplete recovery of peripheral blood counts; QW = once weekly;

For AML = Best overall response is defined as the first response category achieved in the following order: CR_{MRD-}, CR, CRI, MLFS, PR, SD, PD. Response criteria for AML are European LeukemiaNet Response Criteria.

^a Active subjects with days on Study 160 to 448.

^b Only SD > 100 days is included in this table.

Data snapshot date: September 2022.

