4.3.3 Justification of the Monotherapy Recommended Phase 2 Dose (RP2D)

In the current study, **Part 1** and **Part 2** were initially designed to investigate tapotoclax as monotherapy and combinational therapy in subjects with multiple myeloma (MM). As of December 2019, 48 subjects were enrolled in **Part 1** where clinical responses were observed at dose levels $> 240 \text{ mg/m}^2$. At that time, tapotoclax-associated elevations of troponin were observed at dose levels of 360 mg/m^2 and 480 mg/m^2 . Consequently, to avoid the potential for troponin elevations, only doses less than equal to 240 mg/m^2 are currently under investigation. Additionally, monotherapy efficacy of tapotoclax in AML has been limited, with an overall response rate (ORR = CR + incomplete hematologic recovery [CRI]) of 9.4% (3 out of 32 subjects) in monotherapy **Parts 3a, 3b, and 3c** (all responses were CRI). In contrast, increased antileukemic activity has been observed in combination with azacitidine. Consequently, combination therapy has been prioritized in the current study (**Parts 4 and 5**) to optimize the clinical benefit to subjects, and monotherapy investigations were completed to support the combination therapy studies.

As of November 2022, in AML subjects, 2 out of 17 subjects in **Part 3a** (ORR = 11.8%), 1 out of 11 subjects in **Part 3b** (ORR = 9.1%), 0 out of 4 subjects in **Part 3c** (ORR = 0%), and 3 out of 21 subjects in **Part 4** (ORR = 14.3%) have achieved the best overall response of CR or CRI. With the 21 AML subjects who received combination tapotoclax plus azacitidine in **Part 4**, 12 subjects had at least 1 evaluable disease response; 2 subject (9.6%) had CR; 1 subject (4.8%) had CRI; 8 subjects (38.1%) had stable disease (SD); 1 subject (4.8%) had PD (9 subjects [42.9%] did not have an evaluable disease response) (see [Table 2-1](#) for details). Three out of 21 subjects (14.3%) achieved CRI or better in all cohorts in **Part 4**, and 2 out of 6 subjects (33%) achieved CR in tapotoclax 240 mg/m^2 QW plus azacitidine cohort, demonstrating a better response at the 240 mg/m^2 dose compared with lower doses when administered in combination with azacitidine.

Preliminary PK/PD modeling for tapotoclax (monotherapy or in combination with azacitidine) to date have shown subtherapeutic exposures with regard to the estimated minimum efficacious exposures for tapotoclax at doses below 240 mg/m².

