PD ^b	
Any one or more of the following:
 
• Increase of $\geq 25\%$ from lowest response value in:
➢ Serum M-component and/or (the absolute increase must be ≥ 0.5 g/dL)○ Urine M-component and/or (the absolute increase must be ≥ 200 mg/24 h)○ Only in patients without measurable serum and urine M-protein levels; the difference between involved and uninvolved FLC levels. The absolute increase must be > 10 mg/dL➢ Bone marrow plasma cell percentages (absolute percentage must be $\geq 10\%$)• Definite development of new bone lesions or soft tissue plasmacytomas or definite increase in the size of existing bone lesions or soft tissue plasmacytomas^{e, f, g}• Development of hypercalcemia (corrected serum calcium > 11.5 mg/dL or 2.65 mmol/L) that can be attributed solely to the plasma cell proliferative disorder

Page 2 of 2

Source: Durie et al, 2006; Rajkumar et al, 2011 (*modified for protocol purposes*).

CR = complete response; sCR = stringent complete response; FLC = serum light chain; MR = minor response; PD = progressive disease; PR = partial response; SFLC = serum-free light chain; SPEP = serum protein electrophoresis; UPEP = urine protein electrophoresis; VGPR = very good partial response

Note: Patients with measurable disease in both serum (SPEP) and urine (UPEP) at study entry are required to meet response criteria in both UPEP and SPEP in order to qualify for a MR or better. Conversely, it should be noted criteria for PD only needs to be met, and confirmed, in 1 parameter. For patients without measurable protein on UPEP at Baseline, UPEP will need to be repeated to confirm a response.

^a Patients with measurable disease in both serum (SPEP) and urine (UPEP) at study entry are required to meet response criteria in both UPEP and SPEP in order to qualify for a MR or better. Conversely, it should be noted that criteria for PD only needs to be met, and confirmed, in one parameter.

^b All response categories (CR, sCR, VGPR, PR) require 2 consecutive assessments made at any time before the institution of any new therapy, as well as no known evidence of progressive or new bone lesions if radiographic studies were performed. Radiographic studies are not required to satisfy these response requirements. Bone marrow, plasmacytoma, and skeletal survey assessments are not required to be confirmed by repeat testing. SD requires a duration of ≥ 6 weeks.

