### Best Overall Response (BOR):

BOR for a subject is the best observed post-baseline disease response based on investigator assessment.

- AML: BOR is defined as the first response category achieved in the following order: CRMRD-, CR, CRI, MLFS, PR, SD, PD. Response criteria for AML are ELN Response Criteria.
- MM: BOR is defined as the overall response at end of study (data collected on the Best Overall Response CRF). If the overall response is missing, BOR will be derived from the post-baseline disease assessments in the order of: sCR, CR, VGPR, PR, MR, SD, PD. Response criteria for MM are IMWG Uniform Response Criteria.

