Response criteria for clinical trials only		
• Stable disease	Absence of CR MRD -, CR, CRi, PR, MLFS; and criteria for PD not met	Period of stable disease should last at least 3 mo
Relapse		
• Progressive disease (PD) a,b	Evidence for an increase in bone marrow blast percentage and/or increase of absolute blast counts in the blood: 
 
• > 50% increase in marrow blasts over baseline (a minimum 15% point increase is required in cases with < 30% blasts at baseline; or persistent marrow blast percentage of > 70% over at least 3 mo; without at least a 100% improvement in ANC to an absolute level (<math>> 0.5 \times 10^9/L [500/\mu L]</math>), and/or platelet count to <math>> 50 \times 10^9/L [50000/\mu L]</math> nontransfused); or
 
• > 50% increase in peripheral blasts (WBC <math>\times</math> % blasts) to <math>> 25 \times 10^9/L (> 25000/\mu L)</math> (in the absence of differentiation syndrome)b; or
 
• New extramedullary disease
 
	Category mainly applies for older subject given low intensity or single-agent “targeted therapies” in clinical trials. In general, at least 2 cycles of a novel agent should be administered. Some protocols may require blast increase in 2 consecutive marrow assessments at least 4 wk apart; the date of progression should then be defined as of the first observation date. Some protocols may allow transient addition of hydroxyurea to lower blast counts. Hydroxyurea is unapproved for AML in Japan. “Progressive disease” is usually accompanied by a decline in ANC and platelets and increased transfusion requirement and decline in performance status or increase in symptoms.
• Hematologic relapse (after CR MRD -, CR, CRi)	Bone marrow blasts $\geq 5\%$ ; or reappearance of blasts in the blood; or development of extramedullary disease	
• Molecular relapse (after CR MRD -)	If studied pretreatment, reoccurrence of MRD as assessed by RT-qPCR or by MFC	Test applied, sensitivity of the assay, and cutoff values used must be reported; analyses should be done in experienced laboratories (centralized diagnostics)

Page 2 of 2

ANC = absolute neutrophil count; d = day(s); IDH = isocitrate dehydrogenase; MLFS = morphologic leukemia-free state; mo = month(s); WBC = white blood cell; wk = week(s)

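### The SAP's AML best overall response rule ranks any single stable-disease record above progression with no minimum duration, at odds with the 3 months in its own Appendix B

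*SAP*

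**What the plan says.** SAP section 5 gives a general principle, then one rule per disease. The principle is "BOR for a subject is the best observed post-baseline disease response based on investigator assessment". For AML the text continues "AML: BOR is defined as the first response category achieved in the following order", with a list running from MRD-negative CR down through PR, then SD, then PD. It adds "Response criteria for AML are ELN Response Criteria". No minimum duration is given for any category.

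SAP Appendix B sets out those ELN criteria. SD is defined there as no response with the criteria for PD not met, and the comment beside it reads "Period of stable disease should last at least 3 mo".

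Protocol Table 2-1 (section 2.2.2.4) uses the same AML ranking and also cites ELN, but carries a footnote: "Only SD > 100 days is included in this table".

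For MM the SAP says "MM: BOR is defined as the overall response at end of study (data collected on the Best Overall Response CRF"). A ranking of visit assessments, again with SD above PD, is used only when that entry is missing. Protocol Appendix 9 (section 11.9), footnote b, states "SD requires a duration of" at least 6 weeks.

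**The concern.** Best overall response is a ranking over visits. An investigator at the cycle 2 day 1 visit can record only that the subject is stable on that day, so a 3-month condition cannot be met or failed at that visit. It has to be applied when the visits are combined, and the AML derivation does not apply it. Read as written, the rule and the criteria it cites give different answers for the same subject.

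This matters because SAP section 10 drops EFS, PFS and time to response after the early termination. Of the efficacy endpoints in SAP Table 3, that leaves overall response rate and duration of response. Neither says anything about non-responders. If a best overall response summary is produced, its SD and PD rows are where early progression among non-responders would show. Protocol section 2.3.1 cites a median overall survival below 3 months for this population, so 3 months of stability is informative in a way that one stable reading at 4 weeks is not.

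**Working it through.** The plan gives no figure for this rule, so the check applies the rule to the assessment schedule and compares the result with the cited criteria.

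**Inputs**
- Ranking with SD above PD and no duration term: SAP section 5.
- SD of at least 3 months: SAP Appendix B, comment column.
- Response assessment every 28 days, window 7 days either way: SAP section 3.1 and Protocol section 4.1.
- Month length 30.4 days: the time-to-event formulas in SAP section 5 (DOR, EFS, OS, PFS).
- MM SD of at least 6 weeks, which is 6 × 7 = 42 days: Protocol Appendix 9, footnote b.

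**Step 1. The limit in days.** 3 × 30.4 = 91.2 days.

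**Step 2. When assessments fall.** Assessment k is at 28k days after first dose, with a range of 28k − 7 to 28k + 7.

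| Assessment | Nominal day | Window | Reaches 91.2? |
|---|---|---|---|
| 1 | 28 | 21–35 | no |
| 2 | 56 | 49–63 | no |
| 3 | 84 | 77–91 | no |
| 4 | 112 | 105–119 | yes |

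**Step 3. An AML subject with SD at assessment 1 and PD at assessment 2.** Under SAP section 5 the highest-ranked category recorded is SD, so best overall response is SD. From first dose to PD is at most 63 days, which is 91.2 − 63 = 28.2 days short of the limit. Under the Appendix B comment this subject does not have SD as best response.

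**Step 4. Why one day count is needed.** At assessment 3 the latest elapsed time is 91 days, just under 91.2. The SAP's time formulas add 1 day, which gives 92, just over. If the 7-day window is allowed for, the limit becomes 91.2 − 7 = 84.2 days. The nominal third visit is then 84 elapsed days or 85 with the added day, so it falls on either side. The counting convention decides whether the third or the fourth assessment establishes SD.

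**Step 5. What does not move.** In SAP section 5, overall response rate counts PR or better and duration of response covers responders only. Reclassifying a subject from SD to PD changes neither.

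**Step 6. MM fallback.** Take the same pattern of SD then PD. If duration runs to the last SD record it is 28 days (21–35), below 42. If it runs to the PD date it is 56 days (49–63), above 42. The documents do not say which applies, so no breach can be shown for MM; the SAP fallback simply leaves the requirement out.

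**The case against.** The strongest reply is that the SAP names ELN as the AML criteria, so the 3 months comes in by reference. Table 2-1 weakens this. It cites the same criteria with the same ranking, and a footnote was still needed to apply a floor. The reference alone does not tell a programmer to apply one.

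Other points stand and limit the finding:
- The AML 3 months is a recommendation in a comment column and not part of the SD definition itself.
- Best overall response is not a listed endpoint and has no row in SAP Table 3. Only selected analyses are planned for the synopsis report, so the table may not be produced.
- The MM ranking is a fallback behind a CRF entry.

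A reader might go further and infer the size of the effect from the protocol. The azacitidine-combination columns of Table 2-1, with the 100-day floor, show SD in 0/5 + 2/4 + 1/4 + 1/6, or 4 of 19 (21.1%). Protocol section 4.3.3 states no floor and reports "8 subjects (38.1%) had stable disease (SD"), which is 8/21 = 38.1%. This comparison does not measure the effect. The data dates differ (September and November 2022). The two sources also disagree where no SD floor is involved: Table 2-1 has a PR at 180 mg/m² with azacitidine and section 4.3.3 has none, and two responses at 240 mg/m² with azacitidine are CRi in one and CR in the other. Some shorter SD may also have been ongoing at the snapshot.

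A reader might also infer that the rule empties the PD row. Table 2-1 does not support that: it has the floor, yet PD is zero in every column. In its combination columns the rows account for 0 + 3 + 2 + 3 = 8 of 19 subjects, and the other 11 appear in no row.

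**Conclusion.** The AML rule is wrong as written. Taken literally, it gives best overall response SD to a subject whose disease progressed no later than 63 days after first dose, while the criteria it cites ask for about 91 days. This rests on two assumptions: that the sentence is programmed as it stands, and that the Appendix B comment is meant to govern what is reported as SD. The protocol's use of a 100-day floor in Table 2-1 makes the second assumption reasonable.

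The effect is confined to the SD/PD split of a descriptive AML summary, and its size cannot be estimated from the documents. Misclassification is possible, not certain, because a floor could again be added by table footnote. A reader might infer that the case for developing the drug is undermined. The documents do not support that: sections 1.1, 2.3.1 and 4.3.3 of the protocol argue from clinical responses and CR/CRi rates, not from SD. For MM the point is only an omission in a fallback derivation.

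**What to change.** In SAP section 5, under best overall response:

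- **AML.** Count SD as best overall response only if it is documented for at least 3 months from first dose. State this as one fixed day count that allows for the 7-day visit window, and say whether the SAP's added day is included.
- **AML, SD then PD before that limit.** Classify as PD.
- **AML, shorter SD with no later assessment.** Show in a separate row, labelled SD of insufficient duration or not evaluable, so that every subject appears somewhere in the table.
- **MM.** Where the fallback is used, apply the protocol's existing 6-week requirement and state the start and end dates of the interval.

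The cost is a few sentences and a small change to the derivation, with no new data. The SD percentage becomes less favourable. Because Table 2-1 used a 100-day limit and left shorter SD out of every row, the new table will still not match it exactly; a footnote should say so.

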### Duration of Response (DOR)

Duration of response is calculated for subjects who have achieved a response (PR or better). It is defined as time from the first observation indicating a response to the subsequent date of relapse, disease progression or death (due to any cause), whichever is earlier.

DOR time in months: (earliest date of relapse, disease progression or death - date of the first observation of response +1)/30.4

Subjects without relapse, disease progression or death until the analysis data cut-off date will be censored at the last adequate disease assessment date after first response; otherwise, at first response.

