4.1 Overall Design

This is a phase 1, multicenter, open-label dose-escalation study to define the MTD or recommended dose and **maximum tolerated combination dose (MTCD)** as well as the safety, tolerability, PK, PD, and efficacy of AMG 176 administered as monotherapy or in combination with SOC.

A dose-level review team (DLRT) will be responsible for dosing recommendations, which may include escalation to the next nominal or intermediate dose, de-escalation to a lower nominal or intermediate dose; modifications of the ramp-up dosing, alternative dose frequencies, continuation, delay or termination of dosing; or repetition or expansion of a cohort; or determination of recommended dose. For definition of the DLT-evaluation period and DLT-evaluable subject refer to Section [6.2.1.2.1](#).

Cycles of AMG 176 treatment may continue until confirmed progressive disease (PD) (defined by 2017 European LeukemiaNet [ELN] criteria for AML subjects [Section [11.15](#)]), the subject becomes intolerant to the study medication, signs and symptoms of clinical progression are evident as determined by the principal investigator, or the subject withdraws consent. Evaluation of disease response will be performed every 28 days (\pm 7 days) until PD irrespective of cycle duration including dose delays or treatment discontinuation. The disease assessment schedule is independent of treatment schedules.

Ramp-up dosing in cycle 1 will be utilized whenever the AMG 176 target dose level is at 180 mg/m² or higher to mitigate the risk of TLS (see Section [6.1.1](#)).

A safety follow-up (SFU) visit must be performed 30 days (+3 days) after the last dose of protocol-required therapies. Long-term follow-up assessments will occur every 3 months (\pm 14 days) after end of treatment (EOT) for 1 year and include survival, subsequent anti-cancer therapy, and any cardiac associated serious adverse event or studies performed.

The overall study design is described by a study schema in Section 1.2. An overview of the study design is presented in [Table 4-1](#). The endpoints are defined in Section 3.

Table 4-1. Overview of Study Design

Part	Indication	Cohort/Treatment Group	AMG 176 Dose Levels ^{a, b}	Number of Subjects	Design
CLOSED TO ENROLLMENT					

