- Use of known OATP1B1 and/or OATP1B3 substrates with a narrow therapeutic window within 5 half-lives of the drug or its major active metabolite, whichever is longer, following the last dose of the drug prior to enrollment. Refer to prescribing information for concomitant medications.
- Use of known BCRP substrates with a narrow therapeutic window within 5 half-lives of the drug or its major active metabolite, whichever is longer, following the last dose of the drug prior to enrollment. Refer to prescribing information for concomitant medications.

- Use of oral contraceptives (either combined or progesterone only), estrogenic vaginal ring/percutaneous contraceptive patches, or implants of levonorgestrel/Injectable progesterone for the purpose of pregnancy prevention is prohibited in this study as it is not known if there is the potential of inhibition/induction of enzymes that affect the metabolism of estrogens and/or progestins. However, oral contraceptives may be used for the treatment of menorrhagia or other abnormal menstrual bleeding at the discretion of the investigator.

If use of any other prior or concomitant medication or procedure is in question, please refer to prescribing information and/or consult with the Amgen medical monitor.

There are no prohibited therapies and procedures during the 30-day safety follow-up or the long-term follow-up.

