8.2.2.3 Disease Response Assessment in Acute Myeloid Leukemia

Disease response assessments will be based upon review of bone marrow aspirates and/or core biopsies as well as peripheral blood counts. Refer to the 2017 ELN criteria

in Section 11.15 for additional detail. Complete remission/CRi must be established from bone-marrow samples supplemented with neutrophil, platelet, and peripheral blast counts.

In case of transplantation, a CR or CRi must be confirmed within 4 weeks prior to transplantation.

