### Event-free Survival (EFS) for AML

Event-free survival is defined as the interval from the first dose of IP to the earlier date of induction treatment failure, relapse for those who have induction treatment success (e.g., complete remission), or death due to any cause. Censoring is at the last evaluable

post-baseline response assessment; otherwise, at the first dose of IP. The event date for induction treatment failure is assigned as the date of the first dose of IP.

EFS time in months: (event date - first dose of IP date +1)/30.4

Overall Response Rate (ORR)

ORR is the incidence of either PR or better based on investigator assessment. All subjects that do not meet the criteria for response (PR or better) by the analysis cutoff date will be considered as non-responders.

**For MM subjects: The earliest record where PR or better response has to be confirmed by two consecutive same/better response assessments at any time and should be on/before new anticancer therapy start date. sCR, CR, VGPR and PR are considered as PR or better responses.**

**For AML subjects: The earliest record where PR or better response collected does not need to be confirmed by subsequent assessment and should be on/before new anticancer therapy start date. CRMRD-, CR, CRi(CR with incomplete hematologic recovery), MLFS and PR are considered as PR or better responses.**

Overall survival (OS)

OS is defined as the time from first dose of IP date until death due to any cause.

OS time in months: (date of death - first dose of IP date +1)/30.4

Subjects without event will be censored at their last date known to be alive.

Progression-free survival (PFS) for MM

PFS time is calculated as time from first dose of IP date to disease progression date or death due to any cause, whichever is earlier.

PFS time in months: (event date - first dose of IP date +1)/30.4

Subjects without disease progression or death until the analysis data cut-off date will be censored at the last **non-missing evaluable** disease assessment date. **Subject will be censored at last non-NE post-baseline disease assessment before any anti-cancer therapy. If there are no post-baseline disease assessment, then subjects are censored at treatment start date.**

Time to Response (TTR)

Time to response is defined as the time from the first dose of IP until the first documentation of response (PR or better). Only subjects who have achieved a response will be evaluated for TTR.

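### SAP Section 5 stops ORR and myeloma PFS at new anti-cancer therapy but not DOR or AML best overall response, so remission held by a later treatment can be counted in DOR

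*SAP*

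**What the plan says.** **SAP Section 5 (Definitions)**

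- DOR runs from the first response "to the subsequent date of relapse, disease progression or death (due to any cause), whichever is earlier". For subjects with none of these: "Subjects without relapse, disease progression or death until the analysis data cut-off date will be censored at the last adequate disease assessment date". New therapy and transplant are neither events nor censoring points.
- BOR: "BOR for a subject is the best observed post-baseline disease response based on investigator assessment". For AML it takes the best category in the ELN order, with no end of window.
- ORR, AML: the response "does not need to be confirmed by subsequent assessment and should be on/before new anticancer therapy start date".
- PFS, myeloma only: "Subject will be censored at last non-NE post-baseline disease assessment before any anti-cancer therapy".
- EFS, AML: no cut-off at new therapy.

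**Protocol**

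- Section 6.1.7: "There are no prohibited therapies and procedures during the 30-day safety follow-up or the long-term follow-up".
- Section 4.1: response is evaluated every 28 days "until PD irrespective of cycle duration including dose delays or treatment discontinuation".
- Section 8.1.5: long-term follow-up covers survival, subsequent anti-cancer therapy and cardiac information. Disease response is not listed.
- Section 8.2.2.3, AML: "In case of transplantation, a CR or CRi must be confirmed within 4 weeks prior to transplantation".
- Section 8.2.2.1.7 and Appendix 9, myeloma: a response category needs two consecutive assessments, both before any new therapy.

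**What is still to be analysed.** SAP Section 10 drops PFS, EFS and time to response after early termination. DOR and ORR are not on that list. Under SAP Section 9.5.2, time-to-event endpoints with fewer than 10 events may be given as subject-level data only.

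**The concern.** The study has no comparator, so response duration is read directly as activity of AMG 176, alone or with azacitidine. Four endpoints in one section share the same disease assessments, yet two stop at the next therapy and two do not. With PFS, EFS and time to response dropped, DOR is the remaining measure of how long responses last.

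Two things are at stake. Time in remission on a later treatment can enter DOR. And BOR and ORR can disagree for the same AML subject. BOR matters because Protocol Section 4.3.3 uses it to describe activity by part and dose when supporting the choice of 240 mg/m².

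**Working it through.** The plan states no figure on this point, so the check is a comparison of rules followed by illustrations.

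**1. Which endpoints stop at new anti-cancer therapy**

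| Endpoint | Stops? | Still planned? |
|---|---|---|
| ORR | Yes | Yes |
| PFS (myeloma) | Yes | Dropped |
| EFS (AML) | No | Dropped |
| DOR | No | Yes |
| BOR, myeloma | Yes, through the response criteria | Defined, not in SAP Table 3 |
| BOR, AML | No | Defined, not in SAP Table 3 |

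**2. Can the situation arise?** Treatment can end without progression; Protocol Section 7.1 lists a need for alternative therapy as one reason. Section 6.1.7 then bars nothing in follow-up, and Section 4.1 keeps assessments running until progression. So the text allows it. Section 8.1.5 leaves open whether the later AML assessments are actually made.

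**3. One responder followed through transplant (assumed dates).** Response at month 2, transplant at month 4, still in remission at month 14.
- As written: 14 − 2 = 12 months, censored.
- With a cut-off: about 4 − 2 = 2 months, censored.

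Both values are censored, so neither is an observed duration.

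**4. The direction can reverse.** Same subject, but death at month 5.
- As written: 5 − 2 = 3 months, an event.
- With a cut-off: about 2 months, censored.

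The subject's own value is longer as written, but the Kaplan-Meier curve drops at 3 months only under the rule as written.

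**5. BOR against ORR.** An AML subject has stable disease, stops without progression, starts another therapy and is then assessed as CR. BOR is CR; for ORR the subject is a non-responder. For scale, Protocol Section 4.3.3 reports BOR of CR or CRi in 3/21 = 14.3% of Part 4, which reproduces (exact 95% CI 3.0% to 36.3%). One such subject would make it 4/21 = 19.0% (5.4% to 41.9%). In a 6-subject cohort, one subject is 1/6 = 16.7 percentage points.

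**6. Median DOR under assumed switching.** The documents give no switching rate. Assumptions: exponential times; true median DOR 3 or 6 months; 10%, 25% or 50% of responders due to switch at 1 to 3 months if still in remission; median further remission of 12 or 24 months after the switch; 24 months of follow-up; switching unrelated to prognosis; 200,000 simulated responders.

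| True median | Due to switch (did switch) | With cut-off | As written, further remission 12 / 24 months |
|---|---|---|---|
| 3 | 10% (6%) | 3.0 | 3.1 / 3.1 |
| 3 | 25% (16%) | 3.0 | 3.3 / 3.3 |
| 3 | 50% (32%) | 3.0 | 3.7 / 4.0 |
| 6 | 10% (8%) | 6.0 | 6.2 / 6.4 |
| 6 | 25% (20%) | 6.0 | 6.6 / 7.1 |
| 6 | 50% (40%) | 6.0 | 7.5 / 9.0 |

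The median is longer by a factor of 3.1/3.0 = 1.03 up to 9.0/6.0 = 1.50. The upward direction is built in, because remission after the switch is assumed to be longer. This shows how the rule behaves; it does not estimate the effect in this trial.

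**The case against.** **BOR is not an analysed endpoint.** It is absent from the endpoints in SAP Section 2.1 and from SAP Table 3, and the rates in Protocol Section 4.3.3 are background from November 2022. This stands. The BOR gap is a matter of consistency, relevant wherever BOR is reported.

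**Salvage-only responders would not enter DOR.** The natural reading is that a DOR responder is an ORR responder. That is probably intended, but the SAP does not say so.

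**The data may not exist.** Long-term follow-up does not list response, and the AML schedules tie response assessment to cycles. This stands in part. Section 4.1 still says assessment continues after discontinuation, so the protocol needs reconciling.

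**Following responders through later therapy is a legitimate choice.** AML EFS also has no cut-off, and the PFS rule is for myeloma only. True, and for transplant in particular either approach can be defended. But the SAP marks its estimand sections as not applicable, so no such choice is stated, and ORR for the same AML subjects does use the cut-off.

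**Little will be reported.** Protocol Table 2-1 (September 2022) shows 6 CRi + 1 MLFS + 2 PR = 9 AML responders, at most 2 per dose column, so DOR may appear only as a listing. This limits the effect without removing it, since each listed value follows the same rule.

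**The transplant passages conflict.** Section 6.1.7 excludes transplant during the study while Section 8.2.2.3 foresees it. They are compatible if transplant takes place in follow-up, where the exclusion is lifted.

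**Conclusion.** The point holds for DOR, and for BOR in AML. Following SAP Section 5 as written can count time in remission on a later treatment as response duration on study treatment, and can give an AML subject a BOR of CR alongside ORR non-response. Both conflict with the SAP's own handling of ORR, and the DOR rule also conflicts with its handling of myeloma PFS.

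A reader might go further in four ways that the documents do not support:

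- **That the reported response rate is inflated.** ORR already requires the response on or before new therapy.
- **That myeloma BOR is affected.** Its response criteria already require confirmation before new therapy.
- **That AMG 176 always benefits.** A death after transplant counts as a DOR event and can lower the curve.
- **That later remissions have in fact been credited to AMG 176.** The documents do not say how many responders had later therapy, so the text supports only that they can be.

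The size cannot be estimated from the documents. The conclusion assumes that some responders start another therapy while in remission and that their response is still assessed afterwards.

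**What to change.** 1. In SAP Section 5, define the DOR population as the subjects counted as responders for ORR.
2. Restrict AML BOR to assessments on or before the start of new anti-cancer therapy, as for ORR.
3. Censor DOR at the last adequate assessment before new anti-cancer therapy. State whether transplant counts as new therapy. List the uncensored DOR, with the therapy or transplant date, as supportive, so that both versions can be seen.
4. Reconcile Protocol Sections 4.1 and 8.1.5 on whether response assessment continues in long-term follow-up, and state in the SAP which assessments DOR uses.

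The cost is a few sentences and one extra listing. The therapy start date is already needed for ORR, so no new data are required. The downside is that reported DOR may be shorter or more heavily censored, the censoring may be informative because the decision to switch or transplant is related to prognosis, and deaths after new therapy appear only in the supportive version.
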